## 11.2. Assessment of DTG Plasma Drug Concentrations

### 11.2.1. PK Samples: Collection, Storage and Shipping

Blood samples collected for plasma drug measurement will be centrifuged and the plasma frozen at -70°C or lower. Samples will be shipped to the BioAnalytical Laboratory at the Faculty of Associated Medical Sciences (AMS-BAT), Chiang Mai University, in Chiang Mai, Thailand on dry ice following IATA shipping guidelines for analysis. No clinical samples will be stored for future testing and no genetic testing will be performed on samples collected within the study. Remaining samples will be kept in case repeat testing is required but will be destroyed within 6 months of study closure.

### 11.3. Quantification of Antiretroviral Drug concentrations

All antiretroviral plasma concentrations of DTG will be measured using a validated liquid chromatography-triple quadrupole mass spectrometry assay (LC-MS/MS). The method has been validated based on US-FDA guidelines. The laboratory facility participates in the international external quality control (QC) program of the Clinical Pharmacology Quality Control (Precision Testing) program (University at Buffalo, NY, USA) funded by the National Institutes of Health, USA.

### 11.4. Interim PK Analysis: Cohorts 1A and 1B

For the treatment of HIV-infection it is accepted that a drug will provide an effective response in the paediatric population if comparable drug exposures are achieved to those demonstrated to be safe and effective in adults. From a PK perspective, the planned interim PK analysis after Cohort 1A/1B is to select the appropriate multi-dose schedule to be assessed in Cohort 2. The goal is to ensure that neonates are not exposed to sub- or suprathreshold drug exposures following multi-doses of DTG. The primary focus will be to identify a multi-dose schedule for Cohort 2 that will achieve DTG plasma trough and maximum concentrations comparable to those observed in adults and children.

#### 11.4.1. Pharmacokinetic Criteria for DTG Dose Selection for Cohort 2

Pharmacokinetic modelling and simulation analyses using Stage 1 concentration data will inform the multi-dose schedule of the DTG-DT for Cohort 2. The PK targets for the PETITE DTG study are based on published data and aim to be in agreement with the clinical studies conducted as part of the regulatory approvals for various DTG formulations. At steady-state, the geometric mean (%CV) DTG trough concentrations were 1.11 (46) µg/mL and 2.12 (47) µg/mL in adults receiving 50 mg once daily and twice daily, respectively (Table 1). The ongoing IMPAACT 2019 study is assessing the PK, safety, and tolerability of a novel pediatric fixed-dose dispersible tablet of ABC/3TC/DTG in children living with HIV less than 12 years of age [US FDA Investigational New Drug (IND) #141,131]. The IMPAACT 2019 study is being conducted in collaboration with ViiV Healthcare Ltd, the originator pharmaceutical company, which has been responsible for the development and licensing of DTG (54). Weight band dosing is under investigation in the IMPAACT 2019 trial and PK targets used for dose confirmation were established based on adult data: a lower PK target for DTG C24 was set as 60% of the mean concentrations observed in adults receiving 50 mg once daily (e.g., 1.11 x 0.6 = 0.67 µg/mL) and an upper target set as 140% of the mean concentration observed in adults receiving 50 mg twice-daily (e.g., 2.12 x 1.4 = 2.97 µg/mL). We will apply the same lower DTG C24 target of

0.67 µg/mL for the PETITE-DTG study. This  $C_{24}$  target is based on DTG data generated during the developed of DTG by ViiV Healthcare. This PK target is also comparable to the observed  $C_{24}$  values in children in the IMPAACT P1093 and ODYSSEY trials. The DTG  $C_{24}$  in children using the DTG-DT dosed per WHO weight bands ranged from 0.71 to 0.98 µg/mL (**Table 2**).

Extremely high DTG plasma concentrations should be avoided in neonates due to the risk of DTG displacing unconjugated bilirubin from albumin as such elevated unconjugated bilirubin levels could lead to neonatal brain damage (Section 10.7.2). The geometric mean (%CV) DTG steady-state  $C_{max}$  were 3.67 (20) µg/mL and 4.15 (29) µg/mL in adults receiving 50 mg once daily and twice daily, respectively (**Table 1**). The geometric mean (%CV) DTG  $C_{max}$  in children using the DTG-DT ranged from 3.08 (34) to 7.16 (26) µg/mL (**Table 2**). Individual subject DTG  $C_{max}$  values between 12 to 14 µg/mL were observed in children <14 kg receiving DTG-DT and no associated drug toxicity was reported (29). Using the highest  $C_{max}$  and associated variability observed in children, it is estimated that upper 95% CI of  $C_{max}$  values would be 8.5 µg/mL. No clear toxicity cut-off is defined for DTG  $C_{max}$  but we have set an upper  $C_{max}$  limit of 17.0 µg/mL (2-fold above the values observed in children). The choice of this  $C_{max}$  target is based on historical plasma data in adults and children and their associated safety profiles and remains below those shown *in-vitro* to displace unconjugated bilirubin from albumin with normal albumin concentrations. A similar  $C_{max}$  upper target of 18.35 µg/mL is being used in the IMPAACT 2023 trial assessing a novel liquid DTG formulation in neonates developed by ViiV Healthcare (55). As new data become available on DTG in young children and neonates the  $C_{max}$  target may be adjusted lower.

**A multi-dose DTG regimen will be selected that maintains DTG  $C_{24}$  above 0.67 µg/mL and the  $C_{max}$  below 17.0 µg/mL for the majority of neonates. The multi-dose strategy selected for the paediatric solid formulations of DTG after analysis of Cohort 1A/1B will be presented to and agreed upon by the DSMB prior to being studied in Cohort 2.**

Of note, the DTG dosing schedule selected in Cohort 2 could differ by birth weight (e.g., above and below 3000 g).

While not a specific requirement for the selection of the multi-dose strategy the DTG  $AUC_{0-24}$  with the proposed dosing regimen will also be calculated and compared to the target of 35.1 to 134 (µg·h/mL) used in the IMPAACT 2019 study. This exposure range represents the lower 90% CI of the  $AUC_{0-24}$  observed in adults receiving 50 mg once daily and the upper 90% CI for observed in adults receiving 50 mg twice-daily.

### 11.5. Interim PK Analysis after Completion of 50% Enrolment in Cohort 2

An interim PK analysis is planned after 50% of participants have completed the follow-up in Cohort 2. The aim of a multi-dose strategy with paediatric solid formulations is to achieve DTG exposures comparable to those observed in adults and children, i.e., a DTG  $C_{24}$  above 0.67 µg/mL and a  $C_{max}$  below 17.0 µg/mL for the majority of neonates. The proportion of participants with an  $C_{24} < 0.5$  µg/mL ( $EC_{95}$ ) will also be calculated. The DSMB will review the interim PK data in relation to the observed  $C_{24}$  and  $C_{max}$  values and determine if a dose adjustment is required. A different DTG dosing schedule may be selected based on the data available for the remainder of Cohort 2 infants. Any change to the DTG dosing schedule will be agreed upon by the DSMB before implementation.

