## 2. Abbreviations and Definitions

Abbreviation	Definition
3TC	Lamivudine
ABC	Abacavir
AE	Adverse Event
AIDS	Acquired Immune Deficiency Syndrome
ALT	Alanine transaminase
ART	Antiretroviral therapy
ARV	Antiretroviral
AST	Aspartate aminotransferase
AUC	Area under the concentration-time curve
BID	Twice a day
CI	Confidence Interval
CL/F	Apparent oral clearance
Cmax	Maximum plasma concentration during the dosing interval
Cmin	Minimum plasma concentration during the dosing interval
C24	Concentration 24 hours post-dose
CRF	Case report form
CYP	Cytochrome P450
DAIDS	Division of AIDS
DSMB	Data and Safety Monitoring Board
DTG	Dolutegravir
EAE	Expedited adverse event
FAMCRU	Family Centre for Research with Ubuntu
FDA	United States Food and Drug Administration
FDC	Fixed dose combination
GCP	Good clinical practice
HIV	Human immunodeficiency virus
ICF	Informed consent form
ICH	International Conferences on Harmonisation
INSTIs	Integrase Strand Transfer Inhibitors
IQR	Interquartile range
LPV	Lopinavir
LPV/r	Lopinavir/ritonavir (ritonavir-boosted lopinavir)
MedDRA	Medical Dictionary for Regulatory Activities
NAT	Nucleic acid test
NIH	National Institutes of Health

NNRTI	Non-nucleoside Reverse Transcriptase Inhibitor
NRTI	Nucleoside Reverse Transcriptase Inhibitor
NVP	Nevirapine
OD	Once daily
PHPT	Program for HIV Prevention and Treatment
PI	Principal Investigator
PID	Participant identification number
PK	Pharmacokinetic(s)
PMTCT	Prevention of mother-to-child HIV transmission
RTV	Ritonavir
SAE	Serious adverse event
SOP	Standard operating procedure
T1/2	Half life
Tmax	Time of maximum of concentration
UGT	Uridine 5'-diphospho-glucuronosyltransferase
V/F	Apparent volume of distribution
VL	Viral Load
WHO	World Health Organization
ZDV	Zidovudine

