### 5.3. Endpoints

#### 5.3.1. Primary endpoints

- DTG plasma pharmacokinetics parameters: area under the concentration time curve (AUC); maximum plasma concentration ( $C_{max}$ ), apparent clearance (CL/F), and trough concentration ( $C_{trough}$ )
- Occurrence of the following events: adverse events of Grade 3 or higher; treatment-related adverse events of Grade 3 or higher; any adverse events

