Due to the fixed 5 mg DTG dose, and the anticipated slow metabolism in neonates, the multiple DTG dosing schedule will likely require longer dosing intervals during early life compared to older infants (e.g., every 48 or 72 hours compared to every 24 hours (Section 8.2.1). Possible DTG dosing schedules for 5 mg of the dispersible tablet during the first 28 days of life are shown in **Table 4**. The pharmacokinetic modelling and simulation analyses of Stage 1 PK data will support the multi-dose schedule of 5 mg DTG for Cohort 2.

**Table 4:** Potential multi-dose schedules of 5 mg DTG for neonates in Cohort 2 during the first 4 weeks of life.

DTG 5 mg Dosing Schedule	Neonate - Week of Life			
	1	2	3	4
1	Q72 hrs		Q48 hrs	
2	Q72 hrs		Q24 hrs	
3	Q48 hrs		Q48 hrs	
4	Q48 hrs		Q24 hrs	
5	Q24 hrs		Q24 hrs	

*Note: \*A DTG dosing schedule not listed in the table may be selected based on the PK analysis from Stage 1, and may differ by birth weight (e.g., above and below 3000 g)*

If an HIV NAT test result comes back positive for a neonate at any time during the study, the neonate will not receive any further study drugs, come off study and will be treated as per standard of care (any prior PK samples will be included in the analysis).

At the end of study follow-up, HIV negative infants will continue standard of care HIV prophylaxis, if indicated, as per local guidelines.

An interim PK and safety analysis will be performed after 50% of participants have completed Cohort 2 to assess if a dose adjustment is required and to review safety data. Following the DSMB interim review, a different DTG dosing schedule may be selected based on the data available for the remainder of Cohort 2 infants. Any change to the DTG dosing schedule will be agreed upon by the DSMB before implementation.

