### 9.2.3.1. Cohort 2: Screening and Entry visit(s)

The screening and entry visit(s) will take place when the neonate is <7 days of life (Section 9.1). Screening and entry procedures may be performed as one or 2 separate visit(s). At the Entry visit, ZDV prophylaxis will be initiated instead of NVP and continue until DTG is stopped at Day 28 of life. Thereafter, the infant will switch back to NVP from ZDV and continue prophylaxis per national guidelines.

The study team will support the preparation and administration of the 1st dose of the DTG-DT (half-tablet) mixed with water with the parent(s) or caregiver/legal guardian. The exact time of intake will be recorded. The mother will be explained how to prepare and administer DTG at home. Acceptability testing of the DTG-DT will be performed.

Two blood samples will be drawn for PK assessment, one sample immediately prior to administering the 1st DTG dose and another sample at 1-3 hrs post-dose (**Table 5**). It is planned to draw 0.4 mL of blood per time point.

### 9.2.3.2. Cohort 2: Study Visits 2 and Visit 3

It is anticipated that DTG could be dosed every 24, every 48 or every 72 hours, or some other combination, that is expected to achieve target DTG concentrations throughout the first 4 weeks of life. The PK sampling schedule has been designed to cover these different possible dosing scenarios.

After the Entry, Visit 2 can be scheduled at **any time from the 3rd dose of DTG** but before Week 4 of life. The mother will be instructed not to administer the morning DTG dose prior to attending this study visit. On the morning of Visit 2, clinic study nurses and physicians will take a medical history, examine the neonate, and assess adherence. Assessments will include dispensing diary cards to caregivers, reviewing or collecting diary cards and establishing study drug adherence (pill count). The PK assessment should be deferred if the mother/caregiver reports their baby missing any of the previous 3 scheduled doses prior to the PK sampling visit (Section 9.4).

Prior to the morning DTG dose, a blood sample will be taken for pre-dose PK evaluation and then the protocol-specified DTG dose will be administered. The exact time of intake will be recorded. Acceptability testing of the DTG-DT will be performed.

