#### 9.2.3.4. Cohort 2: Visit 5 and Safety Phone call

Study Visit 5 will be performed in Week 4 of life (Day 22 to 28 of life). The mother will be instructed not to administer the morning DTG dose prior to attending this study visit. Medical staff will take a recent medical history from the parent(s) perform a clinical and laboratory safety visit. Adherence assessment and acceptability testing of DTG will be performed. Study required bloods will be drawn at visit 5, including an HIV NAT test. If any tests yield abnormal results, as specified by protocol specific safety criteria (Section 10), we will consult with paediatricians for appropriate management of the neonate.

Two blood samples will be drawn for PK assessment, one sample immediately prior to administering the morning DTG dose and another sample at 1-3 hrs post-dose (**Table 5**). It is planned to draw 0.4 mL of blood per time point.

The administration of DTG will be stopped by day 28 of life, after which local ARV prophylaxis will be continued as per standard of care.

A telephonic safety visit will be conducted 2 weeks after Visit 5 (+/-4 days). Medical staff will once again take a recent medical history from the parent(s). If no issues are reported, the neonate will exit the study at the conclusion of this visit. If any concerns are noted,

the neonate will be brought back for clinical and special investigations as needed. The total study duration for each individual will depend on the age at enrolment and can range from 5 to 6 weeks.

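### The lower PK criterion tests concentration at 24 h, which is mid-interval under Q48h and Q72h dosing, so a schedule can pass with a trough below target

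*Protocol*

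**What the plan says.** **Aim.** Section 11.4 makes it the primary focus to find a schedule that will "achieve DTG plasma trough and maximum concentrations comparable to those observed in adults and children". Section 5.3.1 lists "apparent clearance (CL/F), and trough concentration" among the primary PK endpoints. Section 9.2.3.2 speaks of a schedule "expected to achieve target DTG concentrations throughout the first 4 weeks of life".

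**Limit.** Section 11.4.1 takes the adult once-daily trough of 1.11 µg/mL and multiplies it by 0.6 to get 0.67 µg/mL.

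**Rule.** Section 11.4.1 then states, in bold: "A multi-dose DTG regimen will be selected that maintains DTG" C24 above 0.67 and Cmax below 17.0 µg/mL for the majority of neonates. Section 12.2.4 simulates the candidate schedules, estimates C24 and Cmax, and proposes the best fit to these criteria. Section 11.5 repeats both limits at the interim after half of Cohort 2, adds the proportion with C24 below 0.5 µg/mL (EC95), and has the DSMB judge dose adjustment on the observed C24 and Cmax.

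**Definitions.** The abbreviations list gives C24 as "Concentration 24 hours post-dose". It defines Cmin separately, as the minimum over the dosing interval.

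**Schedules.** Section 9.2.3 expects that "the multiple DTG dosing schedule will likely require longer dosing intervals during early life compared to older infants". Schedules 1 to 4 of the five in Table 4 contain a Q48h or Q72h phase; only schedule 5 is Q24h throughout.

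**Samples.** At Visit 2, "a blood sample will be taken for pre-dose PK evaluation and then the protocol-specified DTG dose will be administered". At Visit 5 there is "one sample immediately prior to administering the morning DTG dose and another sample at 1-3 hrs post-dose". Table 5 also has a last sample at 24–72 h after the Visit 2 dose, with a note that its timing depends on the schedule.

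**The concern.** With once-daily dosing, 24 h after the dose is the end of the interval, so C24 and trough are the same thing. With Q48h or Q72h dosing they are not: concentrations keep falling for another 24 or 48 h. The protocol carries over a once-daily trough value, states a trough aim, and then tests the value at a fixed clock time that is the trough for only one of its candidate intervals. Nowhere is 0.67 or 0.5 applied at 48 or 72 h, and 11.5 does not link its thresholds to the pre-dose samples.

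Two decisions are framed on this quantity: the choice of schedule after Stage 1 and the dose-adjustment review halfway through Cohort 2. The check is most lenient for the longest intervals, where a low trough is most likely. Cohort 2 infants are low-risk and receive zidovudine, so what is mainly at stake is the neonatal dosing recommendation drawn from the trial.

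**Working it through.** **1. The protocol's own figure.** 1.11 × 0.6 = 0.666, which rounds to 0.67 µg/mL. It reproduces.

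**2. From C24 to trough, with no assumption about volume.** With log-linear decline, C(τ) = C24 × 2^(−(τ − 24)/t½). Section 8.2.1 gives a median t½ of 32.8 h for neonatal washout after in utero exposure.

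| Interval | C(τ)/C24 | Trough if C24 = 0.67 | C24 needed for trough 0.67 |
|---|---|---|---|
| Q48h | 2^(−24/32.8) = 0.602 | 0.40 | 0.67/0.602 = 1.11 |
| Q72h | 2^(−48/32.8) = 0.363 | 0.24 | 0.67/0.363 = 1.85 |

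An infant who just meets the rule is therefore below the protocol's own EC95 of 0.5 at the end of either interval.

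**3. When would a schedule pass on C24 and miss on trough?** This needs a model. I used steady-state one-compartment oral dosing, 5 mg:

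C(t) = [D·ka / (V/F·(ka − k))] × [e^(−kt)/(1 − e^(−kτ)) − e^(−ka·t)/(1 − e^(−ka·τ))], with k = ln 2/t½.

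The protocol gives no neonatal V/F or ka. Assumptions: ka = 1/h; V/F = 5/(3.80 − 0.962) = 1.76 L, a rough proxy from Cmax and C24 in the 3 to <6 kg row of Table 2, varied from 1.2 to 2.64 L; maternal dolutegravir ignored.

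At t½ 32.8 h and V/F 1.76 L, C24/trough is 2.74/1.65 (Q48h) and 2.24/0.81 (Q72h), so the typical infant passes either way. Half-lives for which C24 exceeds 0.67 while the trough is below 0.67:

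| V/F | Q48h | Q72h |
|---|---|---|
| 1.2 L | 8.6–16.5 h | 8.7–24.9 h |
| 1.76 L | 10.7–19.7 h | 10.9–29.8 h |
| 2.64 L | 14.0–24.4 h | 14.8–36.8 h |

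Cmax is not the binding limit here: at 32.8 h the highest model Cmax across these cases is about 6.1 µg/mL, against 17.0. The protocol gives 12–14 h for children and adults and no half-life for days 7–28.

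**4. Share of infants.** CL/F is lognormal with a CV of 30% or 50% (the range in 12.1), median t½ 32.8 h, V/F fixed at 1.76 L.

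| | Q48h, CV 30% / 50% | Q72h, CV 30% / 50% |
|---|---|---|
| C24 < 0.5 | ≤0.34% | ≤0.34% |
| Trough < 0.5 | 1.4% / 8.6% | 21.3% / 31.0% |
| C24 < 0.67 | ≤1.0% | ≤1.0% |
| Trough < 0.67 | 4.2% / 14.1% | 37.1% / 41.9% |

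Among the 12 infants at the interim, the Q72h figures mean 12 × 0.213 = 2.6 to 12 × 0.310 = 3.7 with a trough below EC95, nearly all uncounted if C24 is used.

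Over V/F 1.2–2.64 L, C24 < 0.5 is 0–1.5%, while trough < 0.5 is 0.3–17% (Q48h) and 9–47% (Q72h). The majority verdict on 0.67 holds at the trough at 1.76 L (86–96% above for Q48h, 58–63% for Q72h). At 2.64 L it reverses for Q72h: 60–65% have a trough below 0.67, against 0.3–4.6% by C24.

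**The case against.** The best defence is that the intent is already trough: 11.4 says so, the source value is called a trough, and C24 may be shorthand inherited from a once-daily trial. The schedule-dependent last sample in Table 5 supports this. If it is taken at the end of the interval, no 24 h concentration is observed under Q48h or Q72h, and the late value before the DSMB is the end-of-interval one. This shows that the handling at the interim is ambiguous. It does not rescue the rule: the window also allows 24 h, a C24 can be read off a model, and the protocol defines C24 and Cmin separately.

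Several points limit the consequences, and they stand:

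- In the base case the typical trough passes and the majority verdict does not change. Cohort 2 admits infants from 2000 g within 7 days of life, so a V/F below 1.76 L is at least as plausible as one above it; at 1.2 L the typical Q72h trough is 1.19. The 2.64 L bound is only a sensitivity value.
- Table 4 uses Q72h only in weeks 1–2, when clearance is least mature, and maternal drug adds to early concentrations. The shortest half-lives in the windows are remote for that period.
- The EC95 count has no action threshold.
- Section 8.2.1 cites a neonatal simulation study with a lower target of 0.256 µg/mL. The edge-case trough of 0.40 is above it and 0.24 just below. In the base case 0.1–2.6% (Q48h) and 4–14% (Q72h) of infants would have a trough under 0.256.
- Full profiles are simulated, Ctrough is a primary endpoint, troughs are estimated from the final model, and the DSMB must agree the schedule.

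These safeguards make it likely that someone would notice a low trough. They do not make the written criterion detect it.

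**Conclusion.** The criterion is wrong as written. The aim and the derivation of the limit refer to the end of the interval; the decision rule refers to 24 h. For any finite half-life, an infant exactly at the limit on C24 is below it at the trough under Q48h or Q72h, by 40% and 64% respectively at 32.8 h. That part rests only on the protocol's definitions and log-linear decline.

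How often this would matter depends on neonatal V/F, ka and the half-life over days 7–28, which the protocol does not give. In the assumed base case the schedule decision is unchanged, but the EC95 count at the interim would report at most 0.34% of infants where 1–9% (Q48h) or 21–31% (Q72h) are below EC95 at the end of the interval. A wrong schedule is possible, chiefly for Q72h at a larger V/F (typical trough below 0.67 above 2.13 L at 32.8 h) or a shorter half-life. This should be fixed, but it does not threaten the trial.

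**What to change.** In 11.4.1, 11.5 and 12.2.4, apply the 0.67 and 0.5 µg/mL checks to the concentration at the end of the dosing interval in force: C24 for Q24h, C48 for Q48h, C72 for Q72h. At the 50% interim, base them on the pre-dose samples already drawn at Visits 2 and 5. If a mid-interval C24 was really intended, say so and justify using a once-daily trough value there.

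Optionally, and for description only, report AUC over the interval scaled to 24 h (AUC0–τ × 24/τ) beside AUC0–24. The numerical targets remain for the sponsor and DSMB to confirm.

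The cost is protocol wording and an extra line of simulation output. Visits, samples, blood volume and sample size do not change.

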### 8.2.1. Dolutegravir Dosing in Neonates

**No specific DTG dosing guidelines are available for neonates.** Based on the WHO weight band dosing guidelines the DTG dose range is between 0.85 to 1.67 mg/kg for children >4 weeks and weighing between 3 and 5.9 kg. In Cohort 1A, 5 mg of DTG, i.e., half of the scored 10 mg DTG-DT, will be administered to neonates who are ≥14 days and <28 days of life. For a 3 kg neonate, this translates to a 1.67 mg/kg dose, but higher drug exposures are anticipated due to the expected slower metabolism in these younger infants. If the drug exposures following

this single dose are found to be safe, it is planned to administer a single 5 mg dose of DTG to neonates  $\leq 14$  days (Cohort 1B).

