Simulations revealed that among neonates whose mother had taken DTG between 6 hours to 24 hours prior to delivery, a 5 mg DTG dose at 24 to 72 hours after birth maintained median  $C_{max}$  concentrations below the target. These data are also supportive that a single 5 mg DTG dose at >3 days of life proposed in Stage 1 of the PETITE-DTG study will not lead to excess DTG concentrations. **However, it is clear that the timing of the second DTG dose is very important.** For example, if the first dose was administered 48 hours after birth, and a second dose 48 hours later, median  $C_{max}$  were within the target; but administering the second dose 24 hours after the first dose led to a  $C_{max}$  above the target. The optimal DTG dosing strategy for neonates remains to be determined and the data generated in Stage 1 of the PETITE-DTG study will guide the timing of DTG doses for the multi-dose stage in Cohort 2.

Another consideration is the background NVP ARV infant prophylaxis. Nevirapine is an inducer of CYP3A which is one of the metabolic pathways of DTG and therefore concomitant use could impact DTG concentrations. Indeed, a drug-drug interaction study of DTG and NVP in adults revealed that DTG  $C_{max}$ ,  $AUC_{0-24}$ ,  $C_{24}$  were reduced by an average of 8%, 19% and 34%, respectively (38). The oral clearance of DTG was 23% faster with concomitant NVP use (1.12 L/r vs 0.91 L/hr), with the plasma half-life 15% faster. Maximum induction of CYP3A by NVP occurs 2 to 4 weeks after initiation (39, 40). Based on this data it is anticipated that concomitant NVP use could decrease DTG concentrations in neonates. As the future clinical application of DTG in neonates will be without concomitant NVP, determining optimal DTG dosing in neonates in the absence of NVP will provide the most informative data. For this reason, neonates who receive multiple doses of DTG in Stage 2 of the PETITE-DTG study will receive ZDV prophylaxis, instead of NVP, for the duration of the study. Only infants born to virologically suppressed mothers will be enrolled in Stage 2.

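### The 17.0 µg/mL Cmax limit is two-fold over what appears to be a confidence limit for a mean, not over children's individual values, and the selection rule asks only that a majority of neonates stay under it

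*Protocol*

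**What the plan says.** Section 11.4 states the purpose of the Stage 1 PK interim: "The goal is to ensure that neonates are not exposed to sub- or suprathreshold drug exposures following multi-doses of DTG".

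Section 11.4.1 explains that very high concentrations are to be avoided because DTG may displace bilirubin from albumin. It then builds the upper limit. Starting from the highest paediatric Cmax "and associated variability observed in children, it is estimated that upper 95% CI of" Cmax "values would be 8.5 µg/mL". The protocol then sets an upper "limit of 17.0 µg/mL (2-fold above the values observed in children"). Shortly before, the same paragraph reports individual Cmax values of 12 to 14 µg/mL in children under 14 kg on the dispersible tablet, with no associated toxicity.

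The selection rule closes the section. The regimen must hold C24 above 0.67 µg/mL and Cmax below 17.0 µg/mL "for the majority of neonates. The multi-dose strategy selected for the paediatric solid formulations of DTG after analysis of Cohort 1A/1B" (the quote runs on into the sentence about DSMB agreement). Section 11.5 repeats the same standard for the interim after half of Cohort 2. Neither section gives a percentage, and neither treats the safety side differently from the trough side. Section 12.2.4 adds that the schedule best fitting the Section 11.4.1 criteria will be proposed to the DSMB.

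**The concern.** The rule has two parts, a threshold and the share of infants who must respect it. Both are looser than the text suggests.

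The threshold is applied to individual neonates, but its stated two-fold margin appears to be taken over the precision of a group mean. A confidence limit for a mean shrinks as n grows and says little about how high individual children go. A reader of Section 11.4.1 would take 17.0 to be twice what children have experienced, yet the paragraph itself reports children at 12 to 14.

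The share is a majority, which literally means more than half. That is a weak standard for a limit motivated by possible neonatal brain damage, and it does not match the goal in Section 11.4. This rule guides the choice of schedule for the first multi-dose cohort and the decision on changing it at the Cohort 2 interim.

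**Working it through.** **Inputs.** Highest paediatric Cmax 7.16 µg/mL, CV 26% (Section 11.4.1); n=9 in that band, 20 to <25 kg (Table 2). Base of the margin 8.5 and limit 17.0; individual values 12 to 14 (Section 11.4.1). Log-normal values are assumed, with σ = √ln(1+CV²) = √ln(1+0.26²) = 0.256.

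**1. The plan's own figure.**
- Upper 95% confidence limit of the geometric mean: 7.16 × exp(1.96 × 0.256/√9) = 8.46, which rounds to 8.5. Doubling 8.5 gives exactly 17.0.
- Other formulas for a mean come close: 8.72 with t on 8 df, 8.38 arithmetic with z, 8.59 arithmetic with t.

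**2. The same band, for individual children.**
- Log-normal 97.5th percentile: 7.16 × exp(1.96 × 0.256) = 11.8.
- Log-normal 95th percentile: 10.9.
- Arithmetic mean + 1.96 SD: 7.16 × (1 + 1.96 × 0.26) = 10.8.
- t prediction limit: 13.3.

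Only formulas that divide by √9 reach about 8.5. On the log-normal model, 1 − Φ(ln(8.5/7.16)/0.256) = 25% of children in that band would themselves exceed 8.5.

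**3. The margin on individual values.**

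| Comparator | Value (µg/mL) | 17.0 ÷ value |
|---|---|---|
| Figure doubled in Section 11.4.1 | 8.5 | 2.00 |
| 97.5th percentile, 20 to <25 kg | 11.8 | 1.44 |
| Reported individual values, low end | 12 | 1.42 |
| 97.5th percentile, 6 to <10 kg (5.27, CV 50%) | 13.3 | 1.28 |
| Reported individual values, high end | 14 | 1.21 |

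**4. What a majority permits.** The smallest majority of 12 is 7, so 5 may exceed the limit. The smallest majority of 24 is 13, so 11 may exceed it. The same counts apply to C24.

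**5. Boundary illustrations, not forecasts.**
- Suppose exactly half of infants fall below 17.0. The 95th percentile of Cmax is 17.0 × exp(1.645σ): 26, 29 or 37 µg/mL at CV 26, 34 or 50% (the Cmax CVs in Table 2 range from 26 to 50%).
- Suppose exactly half are above C24 0.67. The share below the 0.5 µg/mL EC95 of Section 11.5 is Φ(ln(0.5/0.67)/σ): 25% at CV 46% (adult once-daily, Table 1) and 36% at CV 98% (3 to <6 kg, Table 2).

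**The case against.** **The majority clause is not the whole rule.** Section 12.2.4 picks the best-fitting schedule among several, and Table 4 offers longer intervals. A schedule with nearly half of infants above 17.0 would rarely be the best fit. With the 32.8 h washout half-life of Section 8.2.1 and a peak at about 2 h, a median Cmax of 17 implies C24 of about 17 × exp(−ln2 × 22/32.8) = 10.7, far above 0.67, so a longer interval would fit better. This argument stands: the boundary cases are unlikely, and the two could not occur together in one schedule. It lowers the practical risk but supplies no bound, and Section 11.5 applies the same unquantified standard to observed data.

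**Other safeguards exist.** These are DSMB agreement before Cohort 2 and at the interim, bilirubin testing at Entry and Visits 2, 4 and 5, discontinuation and hold criteria, the AUC comparison, the separate count of C24 below 0.5, and the option to lower the Cmax target. They stand, so a claim that the safety side of the rule does nothing would go too far. The hold and discontinuation criteria rest on events and bilirubin rather than on DTG concentration.

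**A numeric share could sit in the SAP or DSMB Charter.** That would be fair if the protocol were silent. It is not silent: it states a rule, and Section 12.2.4 refers schedule selection back to it.

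**The limit does not rest on 8.5 alone.** Section 11.4.1 also cites safety profiles, in-vitro displacement data and a similar 18.35 µg/mL target in another neonatal trial (IMPAACT 2023). In the lightest band (3 to <6 kg: 3.80, CV 34%, n=8) the individual 97.5th percentile is 7.27, so 17.0 is 2.3 times that. This supports the limit as a choice. It does not rescue the sentence, which speaks of children generally and builds on the highest band.

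**Birth weight is already considered.** Several sections allow schedules to differ above and below 3000 g. They say the schedule may or could differ, and do not require the criteria to be met in each band.

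**Conclusion.** The point holds in two parts. First, the statement that 17.0 µg/mL is two-fold above values in children is wrong for individual values: the margin is 1.2- to 1.4-fold against the values the protocol reports, and 1.44-fold against the 97.5th percentile of the band it used. That 8.5 is a confidence limit of a mean is an inference from the reproduction, since no formula is stated, but no individual-level formula tried comes near it. The mismatch with 12 to 14 needs no model. Second, a bare majority tolerates up to 11 of 24 or 5 of 12 infants beyond the limit and does not match the Section 11.4 goal.

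The percentiles assume log-normality. The 26–37 µg/mL and 25–36% figures only show where the wording would allow matters to go.

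Stronger readings are not supported:
- A reader might infer that 17.0 is unsafe. The protocol reports no toxicity at 12 to 14 and says that no clear toxicity cut-off is defined.
- A reader might see a contradiction with the 7.34 µg/mL upper target in Section 8.2.1. That is the target of a cited modelling study, which the protocol uses to support the single Stage 1 dose. The finding there about a second dose after 24 hours is one example with a first dose 48 hours after birth.
- A reader might infer that the DSMB is being misled. The individual values are disclosed in the same paragraph.

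**What to change.** 1. In Section 11.4.1, state how 8.5 µg/mL was obtained. Correct the two-fold statement so that the DSMB sees the margin on individual values. In the same edit, reconcile the lowest paediatric Cmax, given as 3.08 in the text and 3.80 in Table 2; it does not enter the 8.5.
2. Reconcile the majority wording in Sections 11.4.1 and 11.5 with the goal in Section 11.4. The clinical team and DSMB should fix the required share before Stage 1 data are seen, separately for Cmax and for C24, because the two sides carry different risks.
3. Report upper percentiles of simulated Cmax and the proportion meeting each target, overall and by the birth-weight bands already named (below and above 3000 g). A fixed 5 mg is 5/2 = 2.5 mg/kg at the 2000 g minimum birth weight, against the 0.85 to 1.67 mg/kg cited in Section 8.2.1, so an overall proportion can conceal the lighter infants.

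The concentration limit, the required shares and the schedule remain decisions for the clinical team and DSMB. The cost is a protocol wording change and extra output from simulations already planned. The downside is that fewer schedules may qualify.
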